RFA delivers a large yet focused amount of energy to an area of thyroid tissue that becomes “charred” and thus nonfunctional and nonviable. The residual tissue is slowly resorbed by the surrounding normal tissue, which leads to the resulting shrinkage of the original thyroid nodule (2, 10). Therefore this effect would be very desirable for a cancerous lesion, if it can be achieved safely. Our experience confirms that ultrasound-guided RFA is a clinically effective and safe outpatient treatment in patients with symptomatic or steadily growing benign, large, predominantly solid TNs. With appropriate expertise and world class infrastructure at Mayo Clinic this technique can be extended to treat papillary thyroid carcinomas and has the potential to become an alternative for the management of cancerous papillary thyroid nodules. Hence this pilot study is planned to test this hypothesis and secondarily to identify the safety of RFA for PTC, reveal factors predicting greater response, comparing the performance of RFA with other procedures, and timing of the additional RFA sessions, if needed.

[figure not shown]

Study Design and Procedure

STUDY DESIGN

This will be an open-label clinical trial that will target patients diagnosed with small papillary thyroid carcinoma (<1.5 cm) interested in RFA therapy. They will be assessed clinically and if they are considered candidates for non-surgical choices (observation or percutaneous ethanol injection) these patients will then be offered also the option of RFA therapy. We will treat them with RFA therapy of the PTC lesion and monitor the clinical response through changes in nodule size as measured by ultrasound (> 50% volume shrinkage at 18

Figure 1. RFA for PTC – Overview

months considered positive outcome) and/or development of cervical or distant metastatic disease. We expect that an individual will be thus in the study for a total of 18 months. The schematic depiction of the sequence of events during the trial is presented in figure 1.

The safety of the procedure will be also part of the primary objective, both local reactions as well as complications from RFA. We plan to enroll 5 patients. The study will take place at Mayo Clinic in Rochester, MN. We expect that we would be able to identify 15 cases/year that would qualify for this trial. Given the potential acceptance to enrollment we expect that it would take 18-24 months for the trial completion.

PROCEDURE:

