Enrolled patients will undergo RFA in a single session and then be followed for efficacy and safety of the procedure for 18 months.

Ultrasonography will be performed using a 6- to 15-MHz probe with the GE Logiq E9 ultrasound system. Nodule volume and the percentage of volume reduction are calculated using the following equations: volume= length x width x depth x 0.525; volume reduction percentage = [(initial volume - final volume) x 100%] /initial volume.

Patients will be sedated with general anesthesia during the procedure. General anesthesia is preferred in light of the improved pain control, and the desire to avoid any motion interference that could compromise the accuracy of the technique. A radiofrequency generator (Cool-tip; Covidien) and an 18-gauge, 15-cm electrode with a 1- or 2-cm active tip will be used in the procedure. All radiofrequency procedures will be performed by designated operators under ultrasonographic control with the same scanner model as used for the initial diagnostic evaluation.

For electrode placement, an in-plane oblique approach will be employed as opposed to directly entering the TN using the shortest pathway. The longer oblique pathway is chosen to lengthen the distance between the skin and the active tip of the RF electrode to reduce the chance of skin burns. Steps will be taken to protect extrathyroidal structures from generated thermal energy including selection of needle path, continuous ultrasound monitoring, and potential hydro-dissection if needed to generate a safe margin. Nodules will be selected for treatment that can be expected to be treated with technical success without the zone of ablation extending beyond the margin of the thyroid. Subcapsular lesions may be treated if the thyroid can be confidently isolated from adjacent structures with hydro-dissection. Safety will be paramount. The active tip of the electrode will be kept at a safe distance to prevent a skin burn.

The size and number of RF electrodes, total energy delivered, and total ablation times will be different according to target size and location. Patients will be intensively monitored during RFA and then closely observed for approximately 3 hours after the procedure and released home thereafter, unless adverse effects developed (11, 12).

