
- The study plans to include subjects previously diagnosed with a specific disease and add newly diagnosed subjects in the future.

(5c) The study will use data that have been collected under another IRB protocol. Include in the Methods section and enter the IRB number from which the research material will be obtained. *When appropriate, note when subjects have provided consent for future use of their data and/or specimens as described in this protocol.*

Enter one IRB number per line, add more lines as needed

Data Specimens Data & Specimens _____

Data Specimens Data & Specimens _____

Data Specimens Data & Specimens _____

(5d) This study will obtain data generated from other sources. Examples may include receiving data from participating sites or an external collaborator, accessing an external database or registry, etc. Explain the source and how the data will be used in the Methods section.

(6) Video audio recording: *Describe the plan to maintain subject privacy and data confidentiality, transcription, store or destroy, etc.*

HIPAA Identifiers and Protected Health Information (PHI)

Protected health information is medical data that can be linked to the subject directly or through a combination of indirect identifiers.

Recording identifiers (including a code) during the conduct of the study allows you to return to the medical record or data source to delete duplicate subjects, check a missing or questionable entry, add new data points, etc. De-identified data is medical information that has been stripped of all HIPAA identifiers so that it cannot be linked back to the subject. De-identified data is **rarely** used in the conduct of a research study involving a chart review.

Review the list of subject identifiers below and, if applicable, check the box next to each HIPAA identifier being recorded at the time of data collection or abstraction. Identifiers apply to any subject enrolled in the study including Mayo Clinic staff, patients and their relatives and household members.

Internal refers to the subject's identifier that will be recorded at Mayo Clinic by the study staff.

External refers to the subject's identifier that will be shared outside of Mayo Clinic.

Check all that apply:	INTERNAL	EXTERNAL
Name	X	
Mayo Clinic medical record or patient registration number, lab accession, specimen or radiologic image number	X	

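### Does a forecast of 18-24 months to completion conflict with 18-month follow-up and 15 eligible cases a year?

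*Combined protocol and SAP*

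**What the plan says.** The planning figures are all in the protocol's Study Design section:

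- Target: "We plan to enroll 5 patients".
- Supply: "We expect that we would be able to identify 15 cases/year that would qualify for this trial".
- Time per patient: "We expect that an individual will be thus in the study for a total of 18 months".
- Forecast: "Given the potential acceptance to enrollment we expect that it would take 18-24 months for the trial completion".

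The same section sets the positive outcome as "> 50% volume shrinkage at 18" months (a figure caption splits the sentence in the text). The Procedure section starts the clock at treatment: "Enrolled patients will undergo RFA in a single session and then be followed for efficacy and safety of the procedure for 18 months".

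Three further points bear on the reading. No acceptance rate is given anywhere. The medical-records part of the application form (Category 5) states: "The study plans to include subjects previously diagnosed with a specific disease and add newly diagnosed subjects in the future". The Data Analysis section says that no sample size was calculated and that the analysis is descriptive only.

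**The concern.** The forecast stands beside three figures that seem to rule it out. If each patient is followed for 18 months after ablation, a trial that ends at month 18 must have treated all five on its first day. A trial that ends at month 24 must have treated all five by month 6, which at 15 qualifying cases a year requires most of those approached to accept. The sentence itself makes an allowance for acceptance, which suggests that full uptake was not expected.

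The efficacy criterion is measured at 18 months. If the study, or its grant-funded laboratory tests and coordinator time, stopped on the forecast calendar, anyone treated after month 6 would have no 18-month volume. With five patients, each missing one is 20% of the data.

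**Working it through.** **Inputs (Study Design and Procedure).** N = 5; eligible cases 15/year = 1.25/month; follow-up 18 months from treatment. Acceptance *u* is not given, so it is varied as an assumption.

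**Trying to reproduce 18-24 months as total duration.**
Total = 5/(1.25 × *u*) + 18 months.

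| Assumed acceptance | Accrual (months) | Total (months) |
|---|---|---|
| 100% | 4 | 22 |
| 67% | 6 | 24 |
| 50% | 8 | 26 |
| 33% | 12 | 30 |
| 25% | 16 | 34 |
| 20% | 20 | 38 |

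- Low end: 18 − 18 = 0 months for accrual. It is not reproduced from the stated rate.
- High end: 24 − 18 = 6 months; 1.25 × 6 = 7.5 eligible cases; required acceptance 5/7.5 = 67%.
- So 22-24 months, the upper part of the stated range, is reached at 100% down to 67% acceptance.

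**Clock started at the first treated patient.** Four more are needed: 4/1.25 = 3.2 months, total 21.2 at full acceptance. Required acceptance for 24 months is 4/7.5 = 53%.

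**Already diagnosed patients available at opening.** The size of this pool is not given; 5 to 15 is an assumed range. Required acceptance for 24 months is 5/(7.5 + pool):

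- pool of 5: 5/12.5 = 40%
- pool of 10: 5/17.5 = 29%
- pool of 15: 5/22.5 = 22%

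The 22-month figure is therefore an expected value for new cases only, not a firm minimum.

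**Chance variation.** With Poisson accrual of new cases only, the probability of enrolling at least five in 6 months is 87% at 100% acceptance, 56% at 67%, 32% at 50% and 11% at 33%.

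**Reading 18-24 months as the enrolment period.** The sentence opens with "Given the potential acceptance to enrollment" and directly follows the supply figure, so this reading is natural.

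- 18 months: 1.25 × 18 = 22.5 eligible; 5/22.5 = 22% acceptance; total 18 + 18 = 36 months.
- 24 months: 1.25 × 24 = 30 eligible; 5/30 = 17% acceptance; total 24 + 18 = 42 months.

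No stated input conflicts with this reading. The protocol simply does not print the total.

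**What an actual stop at month 24 would cost.** Patients treated by month 6 number 7.5 × *u*, up to five: 2.5 of 5 at 33% acceptance, 1.5 of 5 at 20%. Both figures need an assumed acceptance rate and an assumed closure. The protocol supplies neither: it sets no calendar closing date, no rule ending follow-up at month 24 and no end date for the funding it names.

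**The case for a change.** The strongest case for a change is that neither reading leaves the sentence sound. As total duration, the low end fails on the stated rate, and the high end needs two in three eligible patients to choose ablation when observation and ethanol injection are also on offer. As enrolment time, completion of the trial is the wrong term, and a reader cannot tell a two-year study from one of three to three and a half years. The pool of previously diagnosed patients has no stated size, and that line may be standard form wording. The protocol does not define the end of study, one Procedure sentence describes monitoring only as lasting up to 18 months, and part of the support comes from a career development grant of unstated length. A sentence or two would settle all of this.

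The ambiguity and the unattainable low end stand. What does not stand is the step to lost endpoint data. An expected duration is not a stopping rule, and the Procedure section commits to 18 months of follow-up after treatment for enrolled patients. A grant that expires on this calendar is conjecture. Replacement figures such as accrual of 6-20 months and a total of 24-38 months would rest on acceptance rates of 67% to 20% that the documents do not contain, so they would exchange one unsupported forecast for another.

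**Conclusion.** No change to the plan is needed. The forecast is loosely worded: read as total duration on new cases alone, its low end is short by 4 months even at full acceptance, and its high end needs about 67% acceptance. Read as enrolment time it needs 17-22% acceptance and is consistent with everything else stated. The range as a whole is not refuted, because acceptance is unknown and patients already diagnosed may be available at opening.

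The result affects scheduling only. The study is a five-patient descriptive pilot, and the forecast feeds no endpoint, analysis, sample size or safety rule. If accrual is slow the study runs longer, and the 18-month measurement is still due for each treated patient. This conclusion assumes that the team follows the stated 18-month commitment rather than treating the forecast as a closing date; nothing in the protocol suggests the latter. If the sentence is revised for other reasons, separating enrolment time from total duration would be a courtesy to the reader.

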To evaluate safety and efficacy of RFA procedure, post discharge from hospital, patients will be asked to fill-in a pain questionnaire to assess any level of pain or discomfort post RFA procedure and contacted by phone in the first 72 hours to assess for the presence of any adverse effects related to the procedure. Moving forward, patients will be contacted in a similar manner approximately every 2 weeks for the first 3 months for the purpose of detecting any adverse effects. Patients will have a face-to-face visit 1 month after the procedure for safety assessment as well. During this visit patients will provide blood sample for laboratory tests (Calcium and thyroid tests TSH, T3, T4, and Tg). Next face-to-face visit will happen at 3 month after the procedure; at this visit patients will provide a small volume of blood to test thyroid receptor antibody. Further in the process, patients will be monitored clinically for up to 18 months post RFA procedure.

Note: For laboratory research a small volume of blood (5 ml) will be drawn from patient prior to and post RFA in the OR. Blood will be processed for Mass Spectrometry analysis to evaluate if high temperature generated from RFA would impart any conformational changes to thyroid hormones and impact biological functions.

Concomitant Interventions

Allowed Interventions

TSH suppression as deemed clinically necessary.

Required Interventions

There are no required medications or interventions during this trial

Prohibited Interventions

There are no prohibited medications or interventions during this trial

Adherence Assessment

Not applicable

Resources: We have the commitment of the Division of Endocrinology and Department of Radiology of Mayo Clinic Rochester that they will support this study. These 2 areas have worked collaboratively in a similar project that has led to the adoption of our current RFA protocol for benign thyroid nodules. We have enlisted the collaboration of a company manufacturing RFA devices, StarMed, with some of the single use RFA instrumentation and partial financial support. The procedure cost will be submitted for clinical cost. Additional support for the project is through a ***Richard F. Emslander Career Development Award in Endocrinology and Nutrition*** Grant awarded to [name] that will be utilized for covering cost of laboratory tests, partial financial support for travel expenses for the patients and PI and study coordinator dedicated time to the project.

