4. **X Tests & Procedures:** Collection of data through noninvasive tests and procedures routinely employed in clinical practice that may include: MRI, surface EEG, echo, ultrasound, moderate exercise, muscular strength & flexibility testing, biometrics, cognition testing, eye exam, etc. (Specify in the study design and procedure section)
5. **X Data** (medical record, images, or specimens): Research involving use of existing and/or prospectively collected data.
6. **Digital Record:** Collection of electronic data from voice, video, digital, or image recording. (Specify in the Methods section)
7. **Survey, Interview, Focus Group:** Research on individual or group characteristics or behavior, survey, interview, oral history, focus group, program evaluation, etc. (Specify in the Methods section)

NIH has issued a *Certificate of Confidentiality* (COC).

Biospecimens – Categories 2 and 3

(2) Collection of blood samples. When multiple groups are involved copy and paste the appropriate section below for example repeat section b when drawing blood from children and adults with cancer.

a. **From healthy, non-pregnant, adult subjects who weigh at least 110 pounds.** For a minimal risk application, the amount of blood drawn from these subjects may not exceed 550ml in an 8 week period and collection may not occur more frequently than 2 times per week.

Blood samples will be obtained; Volume 10 cc per visit.

b. **From other adults and children considering age, weight, and health of subject.** For a minimal risk application, the amount of blood drawn from these subjects may not exceed the lesser of 50 ml or 3 ml per kg in an 8 week period, and collection may not occur more frequently than 2 times per week.

No blood samples will be obtained.

(3) Prospective collection of biological specimens other than blood: NONE

Review of medical records, images, specimens – Category 5

For review of existing data: provide a date range or an end date for when the data was generated. The end date can be the date this application was submitted to the IRB. Example: 01/01/1999 to 12/31/2015 or all records through mm/dd/yyyy.

Date Range: All records through 9/15/2019

Check all that apply (data includes medical records, images, specimens).

(5a) No data will be collected beyond the IRB submission date.

X (5b) The study involves data that exist at the time of IRB submission **and** data that will be collected after IRB submission. Include this activity in the study design section.

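### The readable protocol text schedules calcium only at month 1, so unless Figure 1 adds tests, scheduled data cannot show whether an abnormal value is new since RFA or lasting; the thyroid tests share the gap.

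*Combined protocol and SAP*

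**What the plan says.** All scheduled blood work is described in Study Design and Procedure, under PROCEDURE.

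- **Month 1.** The visit is a safety visit: "Patients will have a face-to-face visit 1 month after the procedure for safety assessment as well". The tests follow: "During this visit patients will provide blood sample for laboratory tests (Calcium and thyroid tests TSH, T3, T4, and Tg". This is the only place in the readable text where calcium is named.
- **Operating room.** The note on laboratory research says that "a small volume of blood (5 ml) will be drawn from patient prior to and post RFA in the OR". The stated use is mass spectrometry: "Blood will be processed for Mass Spectrometry analysis to evaluate if high temperature generated from RFA would impart any conformational changes to thyroid hormones".
- **Month 3.** The text says that "at this visit patients will provide a small volume of blood to test thyroid receptor antibody". No other test is named.
- **After month 3.** Patients are followed clinically to 18 months, with no blood test named.

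The Biospecimens section adds a volume without a list of tests: "Blood samples will be obtained; Volume 10 cc per visit".

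On purpose, STUDY DESIGN says: "The safety of the procedure will be also part of the primary objective", and includes complications from RFA. Research Question and Aims makes change in thyroid hormone levels after RFA one of the things to be studied. STUDY DESIGN also refers to Figure 1 for the sequence of events. That figure is not reproduced in the text available for this review.

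**The concern.** Calcium is the only non-thyroid laboratory test named in the plan, and it is placed at a visit held for safety. To call an abnormal result new, one needs a value from before RFA. To call it lasting, one needs a later value. The written schedule gives neither. A pre-existing abnormality, a passing change and a lasting change would all appear as the same single month-1 number. A fall that stays within the normal range would not appear at all.

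The study has one arm, so there is no concurrent group to show what calcium does without RFA, and each patient's own earlier value is the natural comparator. None of the ten readable exclusion criteria concerns calcium or parathyroid disease, so patients with an unrelated abnormality are not screened out by the written criteria.

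For the thyroid tests the consequence is more direct. TSH, T3, T4 and Tg are also named only at month 1, yet the stated aim is to study change. A baseline that is not taken before the procedure cannot be taken afterwards.

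**Working it through.** The plan gives no figure to reproduce here: the Data Analysis Plan is descriptive and no sample size was calculated. The check is a count of scheduled values, followed by one illustration.

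**Step 1: the blood draws in the readable text (all from PROCEDURE).**

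| Time | Stated use | Calcium named? | TSH, T3, T4, Tg named? |
|---|---|---|---|
| Before RFA, operating room | Mass spectrometry of thyroid hormones | No | No |
| After RFA, operating room | Same | No | No |
| Month 1 | Calcium and thyroid tests | Yes | Yes |
| Month 3 | Thyroid receptor antibody | No | No |
| After month 3, to month 18 | No blood test named | No | No |

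The mass spectrometry is described as a study of hormone conformation, so it is not a stated baseline for the month-1 assays.

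**Step 2: what the count allows.** Scheduled calcium values per patient are 0 before RFA, 1 at month 1 and 0 later. A within-patient change needs at least 2 values, one of them before RFA. Persistence needs a value after the abnormal one. With 0 + 1 + 0 = 1 value, neither can be derived from scheduled data. The same count applies to TSH, T3, T4 and Tg.

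**Step 3: how often the question could arise (illustration only).** The documents give no rate of out-of-range calcium unrelated to RFA, so the per-patient rate p is assumed. With n = 5 (Subject Information, target accrual) and independent patients, the chance of at least one such patient is 1 − (1 − p)^5.

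- p = 0.02: 1 − 0.98^5 = 1 − 0.904 = 0.096, or 9.6%.
- p = 0.05: 1 − 0.95^5 = 1 − 0.774 = 0.226, or 22.6%.
- p = 0.10: 1 − 0.90^5 = 1 − 0.590 = 0.410, or 41.0%.

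These are chances that a value needing a comparator occurs at all. They are not chances of a wrong classification, which would also require that no chart value, repeat test or clinical judgement settled the matter.

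**Step 4: blood volume.** If the operating-room note means 5 ml before and 5 ml after RFA, that visit uses 5 + 5 = 10 ml, which is the whole of the stated 10 cc. If it means 5 ml in total, 5 ml remain. The text does not say which, and it describes the month-3 volume only as small.

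**The case against.** The strongest reply is that the readable text is not the whole plan. Figure 1 is the likeliest place for baseline and follow-up tests, and its absence here is not a fault of the protocol. A reader might infer that calcium is measured once in 18 months and that no pre-RFA value will exist. The documents do not support that: they show only that the written text names none. This part of the objection stands, and the point is conditional on Figure 1.

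Other data are also in scope. The Research Activity section covers existing and prospective records. Candidates are assessed clinically and judged for anesthetic risk. After RFA there are calls about every two weeks for three months, a month-3 visit and clinical monitoring. A chart calcium may exist, and nothing forbids repeating an abnormal result. This also stands, but only in part. The plan does not say that such a value will be collected. The date range given for existing records ends on 9/15/2019, before the protocol date of 10/2/2019, and although later data collection is ticked, calcium is not named there.

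A reader might also infer that one abnormal calcium would move the complication proportion by 20 percentage points (1/5). No section counts an out-of-range calcium as a complication, so that figure would rest on a rule the plan does not contain.

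Finally, this is a five-patient descriptive pilot, and the protocol selects nodules so that ablation stays within the thyroid margin. That limits the weight of the point. It does not remove it, because with five patients and no control arm each patient's course is the evidence.

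**Conclusion.** The point holds in a limited, conditional form. In the readable text, calcium and the four thyroid tests are each scheduled once, at month 1. Unless Figure 1 lists other tests, scheduled study data cannot show whether an abnormal calcium is new since RFA or lasting, cannot show a within-range fall, and cannot give the change in thyroid hormone levels that the aims call for. The thyroid part matters more, because change there is a stated aim. Calcium matters because complications belong to the primary objective.

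The size is the count itself, one scheduled value where change needs two and persistence needs a later one. The range of 9.6% to 41.0% rests wholly on assumed rates of 2% to 10% and on independence between patients, and shows only that an uninterpretable value among five patients is not remote. The point does not show that the trial will misreport safety. It is a cheap improvement worth making before the first procedure.

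**What to change.** In PROCEDURE, add calcium, TSH, T3, T4 and Tg to the pre-RFA sample and to the month-3 sample. If Figure 1 already lists these tests, or the chart is meant to supply them, say so and make the text match.

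In the Data Analysis Plan, add a listing of each patient's pre-RFA, month-1 and month-3 values with the change from pre-RFA. The planned median is the third-ranked of five values and stays in range with up to two abnormal patients, so it cannot replace the listing. Describe a value that is in range before and out of range afterwards as new after RFA, and state whether it is still present at month 3. Note separately any worsening of an abnormal baseline. Leave attribution to the investigator's adverse event assessment, since timing alone does not establish cause. The listed changes also make within-range falls visible.

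Cost: 2 × 5 = 10 extra calcium assays and, if the thyroid tests are included, 4 × 2 × 5 = 40 thyroid assays, all at draws already planned. No visit or patient is added. The stated 10 cc per visit may need updating if 5 ml is drawn both before and after RFA.

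### Thyroid receptor antibody is named only at month 3, so on the readable text a positive result cannot be classed as new since RFA or pre-existing

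*Combined protocol and SAP*

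**What the plan says.** The antibody appears once in the protocol text, in the follow-up paragraph under PROCEDURE, which is introduced as assessing both the safety and the efficacy of RFA. The visit is fixed by "Next face-to-face visit will happen at 3 month after the procedure", and the test by "at this visit patients will provide a small volume of blood to test thyroid receptor antibody".

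The other blood work described is:

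- Month 1: "laboratory tests (Calcium and thyroid tests TSH, T3, T4, and Tg"). The receptor antibody is not in this panel.
- Day of the procedure: "a small volume of blood (5 ml) will be drawn from patient prior to and post RFA in the OR". The stated use is mass spectrometry: "Blood will be processed for Mass Spectrometry analysis to evaluate if high temperature generated from RFA would impart any conformational changes to thyroid hormones".
- After month 3: "patients will be monitored clinically for up to 18 months post RFA procedure", with no repeat antibody test named.

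STUDY DESIGN describes the safety aim as follows: "The safety of the procedure will be also part of the primary objective, both local reactions as well as complications from RFA". Target accrual is 5 patients, open label, with no control group. Data Analysis plans descriptive statistics only, with proportions for categorical variables, and does not define new-onset positivity.

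**The concern.** A single post-treatment value gives the proportion positive at month 3. It does not give the proportion who became positive after treatment. If the test is meant to say anything about what follows RFA, the second quantity is the one needed, and it requires a reference value for each patient or a comparison group. The readable text supplies neither.

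The resulting error could go in either direction. A patient who was positive before treatment could be counted as a safety finding, or a patient who became positive after treatment could be set aside as probably pre-existing. With 5 patients, the classification of one person moves the reported proportion by a fifth. The gap also cannot be closed later: after ablation, a pre-RFA value exists only if it was measured earlier or if blood was kept.

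**Working it through.** The plan states no figure for the antibody, so there is none to reproduce. The check is mainly a search of the text for a reference value, followed by an illustration of size.

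**1. Possible sources of a reference value**

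| Source | What the readable text provides |
|---|---|
| Baseline laboratory panel | None described |
| Pre-RFA draw in the OR (PROCEDURE, Note) | Taken, but assigned to mass spectrometry of thyroid hormones |
| Month 1 panel (PROCEDURE) | Post-RFA, and without the antibody |
| Eligibility (Subject Information) | Ten exclusion criteria with text, none on antibody status or autoimmune thyroid disease; item 11 has no text in the available copy |
| Control group (STUDY DESIGN) | None |
| Existing records (Review of medical records) | Use is allowed through 9/15/2019, but no antibody value is required |
| Figure 1 (schematic of events) | Not shown; content unknown |

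Only the last two rows could supply a pre-RFA value. The first of these does so by chance, and the second cannot be checked.

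**2. What each month 3 result would mean**

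- Negative: no positivity at that time. No baseline is needed to say this.
- Positive, with no earlier value: either negative before RFA and positive now, or positive all along. The two cannot be told apart.

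**3. Size of one positive**

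1/5 = 20%, with exact (Clopper-Pearson) 95% interval 0.5% to 71.6%. Without a pre-RFA value this describes prevalence at month 3.

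**4. Chance that the ambiguity arises from pre-existing positivity**

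Let p be the proportion positive before RFA. The documents do not give p, so the values below are assumptions. For 5 independent patients, P(at least one positive before RFA) = 1 − (1 − p)^5.

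| Assumed p | (1 − p)^5 | P(at least one of 5) |
|---|---|---|
| 1% | 0.951 | 4.9% |
| 2% | 0.904 | 9.6% |
| 5% | 0.774 | 22.6% |
| 10% | 0.590 | 41.0% |

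Each such patient adds 20 percentage points to the month 3 proportion, provided that all 5 are tested and the positivity persists to month 3.

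**The case against.** Several objections have force.

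- **Figure 1 may already schedule baseline tests.** This stands. A reader might infer that the plan has no pre-RFA antibody value at all, but the documents do not support that conclusion while the schematic is unavailable. The finding is about the text.
- **The protocol never says why the antibody is measured.** This also stands. The aims do not mention it, and STUDY DESIGN describes safety in terms of local reactions and complications. Treating it as a safety marker is an inference from the paragraph in which the test appears. However, no other purpose is given, and for any question about change after RFA a lone positive is equally ambiguous.
- **A baseline test would not show that RFA caused the antibody.** Correct. A reader might infer that negative-then-positive means RFA-induced. In one arm of 5 patients it shows new onset after RFA and no more.
- **Records may hold an earlier value.** Possible, since patients come from those evaluated for thyroid nodules and existing data may be used. Nothing requires the value to exist, to be recent or to come from the same assay.
- **This is a descriptive pilot, and no decision rule uses the antibody.** True, and it keeps the severity low. It does not remove the point, because a descriptive proportion still has to describe the intended quantity.
- **The prevalence range is assumed.** True. It runs from unlikely to substantial and does not establish importance. The ambiguity of a positive result does not depend on p.

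**Conclusion.** The point holds for the readable text, with limited weight. A negative month 3 antibody result is interpretable. A positive one cannot be classed as new since RFA or pre-existing unless Figure 1 schedules a baseline test or the patient's record happens to contain one. One such patient would appear as 20% positive. The chance that at least one of 5 was positive beforehand is 4.9% to 41.0% for assumed background rates of 1% to 10%.

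The conclusion rests on two assumptions: that the unseen schematic adds no antibody test, and that the test is meant to inform about the period after RFA. Tumour response, the other safety assessments and patient protection are unaffected. It is a cheap improvement of low severity, worth making before enrolment because the missing value cannot be recovered afterwards.

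**What to change.** First check Figure 1. If it already lists a pre-RFA antibody test, state that in the PROCEDURE text and add only the reporting rule below.

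Otherwise, amend PROCEDURE in three respects:

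1. **Test.** Measure the same receptor antibody by the same assay before RFA, on an aliquot of the pre-RFA OR draw, or on a small added volume at that draw if 5 ml does not suffice. The documents do not say whether the research sample suits the assay, so the laboratory should confirm this.
2. **Cheaper alternative.** Store the aliquot and test it only if month 3 is positive. This classifies every month 3 positive. It leaves the baseline status of month 3 negatives unknown, so the denominator is then all patients tested at month 3, not those known to be negative beforehand.
3. **Reporting.** Give new-onset positivity (negative before, positive at month 3) separately from pre-existing positivity, and describe it as new onset after RFA, not as RFA-induced. State in one sentence why the antibody is measured.

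The cost is at most 5 extra assays, plus slightly less sample for mass spectrometry or a slightly larger draw. If the 5 ml applies to each of the two OR draws, they total 2 × 5 = 10 ml, which already equals the 10 cc per visit given under Biospecimens. An added volume would then need that figure changed as well; an aliquot would not.
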